### 11.2 Sample Size Considerations:

The study will be powered to the primary endpoint of clinical improvement with 560 participants included in the according-to-protocol analysis population at Day 5. To achieve this sample size, approximately 674 enrolled subjects will need to be randomized (1:1) to placebo or azithromycin treatment to have 80% power to rule out a 12.5% increase in the clinical improvement rate with antibiotic therapy compared to placebo assuming a clinical improvement rate of 57.6% in each group using a two-sided 95% confidence interval with continuity correction, in a per-protocol analysis (i.e., allowing for 16.9% loss in each treatment group to follow up/rescue medication).

The primary analysis will include an intention-to-treat (ITT) estimation of the difference in proportions of subjects with clinical improvement at Day 5 in the antibiotic and placebo groups with a two-sided 95% confidence interval.

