5. SAMPLE SIZE CONSIDERATIONS

The null hypothesis corresponding to the primary analysis if this study is:

Null hypothesis: $\pi_{\text{placebo}} - \pi_{\text{azithromycin}} \leq -12.5\%$,

Alternative hypothesis (non-inferiority): $\pi_{\text{placebo}} - \pi_{\text{azithromycin}} > -12.5\%$,

where π represents the probability of clinical improvement at study day 5. 12.5% is the non-inferiority margin used for this study.

The study was first designed assuming that 840 subjects would have to be enrolled in order to randomize 420 (50%) subjects and have 80% power to rule out a 12.5% increase in the clinical improvement rate with antibiotic therapy compared to placebo assuming a clinical improvement rate of 80% in each group using a two-sided 95% confidence interval (CI) using normal approximation with continuity correction with continuity correction, in the according-to-protocol analysis population at D5V (ATP-5) as defined in Section 6.3 (i.e., allowing for 15% loss in each treatment group).

These assumptions underlying the original target sample size of 420 subjects were assessed by a planned, interim, blinded analysis after approximately 210 subjects completed or terminated from the study. The interim report was finalized on January 9th, 2020. The observed clinical improvement rate at the time of the interim analysis was 57.6% in each group which is lower than the initially assumed 80% rate. Due to this finding, new sample size estimates have been generated to account for actual observed rates of clinical improvement and protocol deviations that preclude inclusion in the primary analysis. The total sample size was increased to enroll 674 subjects which will allow 560 subjects eligible for the ATP-5 analysis population allowing for 16.9% loss in each treatment group to follow up/rescue medication. This new sample provides 80% power to rule out a 12.5% increase in the clinical improvement rate with antibiotic therapy compared to placebo assuming a clinical improvement rate of 57.6% in each group using a two-sided 95% CI with continuity correction, in an according-to-protocol analysis (i.e., allowing for 16.9% loss in each treatment group to follow up/rescue medication).

Although analysis using an ATP population was used for determination of sample size (to account for missing data), the primary analysis will be an ITT analysis using all randomized subjects.

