8.1.1. Primary Analysis of Clinical Improvement at D5V Using ITT Population

The hypotheses corresponding to the primary analysis of this study are:

Null hypothesis: $\pi_{\text{placebo}} - \pi_{\text{azithromycin}} \leq -12.5\%$,

Alternative hypothesis(non-inferiority): $\pi_{\text{placebo}} - \pi_{\text{azithromycin}} > -12.5\%$,

where π represents the probability of clinical improvement at study D5V. 12.5% is the non-inferiority margin used for this study and is also used for all secondary non-inferiority analyses. The primary analysis alone will be used to conclude non-inferiority of placebo to azithromycin, while other analyses are supportive.

The non-inferiority of placebo versus azithromycin with respect to clinical improvement on at D5V using a non-inferiority margin of 12.5%, will be determined for the ITT analysis population using a two-sided 95% CI of the difference in proportions of clinical improvement as constructed using multiple imputation of clinical improvement with linear regression. The study day that D5V occurred on will be included as a covariate. A lower bound of the CI greater than -12.5% will result in the conclusion of non-inferiority of placebo. The imputation model will utilize available information collected at baseline and any completed study visits.

The primary analysis will use multiple imputation with a linear regression model without rounding to impute missing values of clinical improvement at D5V using the ITT population [9 and 10].

Although the linear regression without rounding can sometimes yield implausible imputed values of treatment success, Horton et.al (2003) [10] showed that this method yields an unbiased estimate of the binomial proportion.

- Let Y_1, Y_2, \dots, Y_N be independent and identically distributed (iid) Bernoulli random variables
- Let $p = E(Y_i)$ be the probability of success
- Assume that only n out of the N Bernoulli data points are observed; the rest are missing. For simplicity, assume Let Y_1, Y_2, \dots, Y_n are observed and Let Y_{n+1}, \dots, Y_N are missing. Further assume that data is Missing Completely at Random (MCAR).

For estimating p , the minimum variance unbiased estimate (MVUE) of p denoted by \hat{p} which is simply the mean of observed data, i.e.,

$$\hat{p} = \frac{1}{n} \sum_{i=1}^n Y_i$$

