Step 3: The final clinical improvement estimates will be obtained by combining M estimates of composite cure estimates using PROC MIANALYZE as described in in Section 8.4.1. The difference in rates of clinical improvement for placebo compared to azithromycin ($p_p - p_a$) when study day of D5V is 5 will then be obtained by β_1 . The rate of clinical improvement for placebo will be estimated as $p_p = \beta_0 + \beta_1$ and the rate of clinical improvement for azithromycin will be obtained by $p_a = \beta_0$ when the study day for D5V is 5. The two-sided 95% CI for the rates of clinical improvement and difference in rates in clinical improvement will use estimates from the linear regression with multiple imputation.

Rates of clinical improvement for each treatment group along with their 95% CI, a point estimate of the difference in rates of clinical improvement at D5V along with 95% CI obtained from linear regression with multiple imputation model as described above will be provided in Table 21 for D5V using the ITT analysis population.

The null hypothesis will be rejected and non-inferiority of placebo versus azithromycin with respect to clinical improvement on at D5V using a non-inferiority margin of 12.5% will be concluded if the lower bound of the 95% CI for the difference in rates of clinical improvement for azithromycin relative to placebo is greater than -12.5%. An individual listing of observed values of clinical improvement is provided in Listing 16.

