8.4. Imputation of Missing Data

8.4.1. Multiple Imputation of Missing Values of Clinical Improvement on Day 5, Day 11, and Day 28

Primary and secondary analyses using the ITT population depend on multiple imputation of clinical improvement on D5V, D11V, and D28V. First, a table showing the number and percentage of missing data for clinical improvement on D5V, D11V, and D28V will be presented in Table 20. Regardless of the percent of missingness, multiple imputation will be used for all ITT analyses. Robustness of the multiple imputation

model will be assessed by tipping point analyses. The results of this sensitivity analyses will be provided in [Table 27](#) for D5V, [Table 28](#) for D11V and [Table 29](#) for D28V. In order to use the MI model to adjust for bias caused by missing data, we assume that data is missing at random (MAR).

For missing clinical improvement on D5V, D11V, or D28V, multiple imputations of missing clinical improvement on D5V, D11V, or D28V will be performed independently, and each subject will have their missing clinical improvement imputed independently of other subjects' imputations using a subject-specific imputation model. The pseudocode shown below details how missing data for clinical improvement for D5V (D11V or D28V) will be imputed using m multiply imputed datasets from linear models. The following covariates will be used non-missing for the MI model: treatment group, site indicators, age, gender, study day of D5V (centered at 5), presence of fever on Day 1, and presence of fever on D5V. The number of imputed, m , datasets will be chosen based on the average percent of missing data. Default value will be $m=20$ since sample size calculation assumed close to 20% drop-out rate.

As a first step to multiple imputation, an ordered list of variables to include in the subject-specific imputation model is constructed. Ordering is specified so that exact imputation results from final data are prespecified may be replicated in SAS (using seeds described below). The complete ordered list of variables for the imputation models for clinical improvement is below:

- Treatment Group (azithromycin is reference)
- Indicator of subject enrolled at the site with the second most number of subjects enrolled (binary indicator)
- Indicator of subject enrolled at the site with the third most number of subjects enrolled (binary indicator)

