- Indicator of subject enrolled at the site with the fourth most number of subjects enrolled (binary indicator)
- Indicator of subject enrolled at the site with the least number of subjects enrolled (binary indicator)
 - Note: the site with the most number of subjects enrolled is reference for site. Language is written to allow for an arbitrary number of sites. In the event of a number of ties for the number of subjects enrolled, tied sites will be ordered in ascending alphanumeric order in the list of model variables.
- Age at enrollment
- Gender (Male is the reference)
- Study day of D5V (centered at 5)
- Presence of fever on Day 1 as recorded on the Assessment of LRTI Symptoms and Fever (LRT) form
- Presence of fever in the day preceding or at the D5V as recorded on Solicited Events or vital signs form

The actual list of MI model variables for each subject-specific imputation model will follow the ordering above but omit variables with missing values. The below pseudo-code / SAS code outlines the creation of 20 multiple imputation datasets. Note that the seeds used in the actual analysis must follow the specification given in the pseudo-code and subjects must be processed in the order described in the pseudo-code. The pseudo-code is for D5V, but the general logic is also applicable to D11V and D28V.

*Outcome variables: clinimprove_D5V

DEFINE i=index variable for subjects having clinical improvement imputed.

Subjects requiring imputation are sorted in ascending order by PATID.

DEFINE N=number of subjects requiring imputation

DEFINE g&i=analysis dataset containing predictors and clinical improvement for

ATP-5 subjects as well as subject i (only one subject not in ATP-5 included). Note that ATP-5 subjects that are missing a value for one or more variables in the subject-specific imputation model are excluded.

DEFINE imp_g&i = g&i, with 20 imputed values for the missing clinical improvement

added by PROC MI

DEFINE &&modelVars_&i = list of observed variables in subject i (treatment group, site1, site2, site3, site4, age, gender, cstday5, fever), to be used for imputation of clinical improvement

Step 1: Imputation model: This model will generate 20 datasets with each dataset containing original complete data along with imputed values for subjects with missing endpoint.

```
%do i=1 %to &N;
```

```
PROC MI data= g&i out= imp_g&i seed= 22131&i NIMPUTE=20 noprint;
```

```
  Var &&modelVars_&i clinimprove_D5V;
```

```

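### With 20 imputations the primary lower bound carries about 0.3 to 0.5 points of avoidable simulation noise, and SAP 8.4.1 both leaves m open and fixes it at 20

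*SAP*

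**What the plan says.** SAP 8.1.1 makes one comparison decisive. Non-inferiority of placebo is concluded "if the lower bound of the 95% CI for the difference in rates of clinical improvement" lies above -12.5%, and other analyses are supportive. The bound comes from multiple imputation in the ITT population, which 8.4.1 applies whatever the amount of missing data.

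On the number of imputations, SAP 8.4.1 says two things:

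- The narrative says the number of "datasets will be chosen based on the average percent of missing data", without a formula, and adds: "Default value will be $m=20$ since sample size calculation assumed close to 20% drop-out rate".
- The pseudo-code and its surrounding text use twenty datasets at every step, with "NIMPUTE=20 noprint" in the PROC MI call.

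The same section fixes the seed for each imputed subject (22131 followed by the subject's index) and the processing order (ascending PATID), and requires the actual analysis to follow both. SAP 8.2.8 and 8.4.2 fix m at 20 for DOOR. Neither document sets a tolerance for Monte Carlo error.

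**The concern.** After multiple imputation the lower bound is partly random. Each missing outcome is replaced by draws from a normal model whose residual standard deviation is about 0.49 (the square root of 0.576 × 0.424), and 20 sets of draws leave visible noise in both the pooled difference and its standard error. Matching m to the expected dropout percentage does not control how far the bound would move under other draws. With a sharp cut-off at -12.5%, a borderline trial could be decided by that noise.

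The wording conflict is a second, smaller matter. If m were changed once the missing rate was known, as the narrative allows, the imputations would be redrawn and the primary bound would move.

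**Working it through.** **Inputs.** Protocol 11.2 gives 674 randomized 1:1 (337 per arm) and 560 evaluable, so (674 − 560)/2 = 57 lost per arm, and 57/337 = 16.9%. I use this as the missing fraction and show 10% and 20% beside it. The improvement rate comes from SAP 5 ("assuming a clinical improvement rate of 57.6% in each group"), so σ² = 0.576 × 0.424 = 0.2442. The margin is in SAP 8.1.1: "12.5% is the non-inferiority margin used for this study".

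**Step 1: the plan's own figure.** Protocol 11.2 sizes the trial "to have 80% power to rule out a 12.5% increase in the clinical improvement rate with antibiotic therapy", "using a two-sided 95% confidence interval with continuity correction, in a per-protocol analysis". Power = Φ[(0.125 − k/n)/√(2σ²/n) − 1.96], where k/n is the continuity correction. With k = 2 and n = 280: (0.125 − 0.0071)/0.0418 − 1.96 = 0.86, so power is 80.6%. The smallest n reaching 80% is 277 per arm (554 in all). Power at 280 would be 82.8% with k = 1 and 84.9% with no correction. 560/(1 − 0.169) = 673.9, which rounds up to 674. The stated size is reproduced.

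**Step 2: between-imputation variance B of the difference, 16.9% missing.**

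- Ordinary joint imputation: B = 2 × (57/337)² × σ² × (1/280 + 1/57) = 2 × 0.0286 × 0.2442 × 0.0211 = 2.95 × 10⁻⁴.
- The SAP's scheme, with a separate parameter draw for each missing subject: B ≈ 2 × 0.0286 × 0.2442 × (1/57)(1 + 1/280) = 2.46 × 10⁻⁴.

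**Step 3: Monte Carlo SD of the lower bound at m = 20.** SD = √[B/m + 1.96² × Var(SE)], with SD(SE) ≈ (1 + 1/m) × B × √(2/(m − 1)) / (2 × SE).

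- Joint: the complete-data variance is 2σ²/337 = 0.00145. Total variance is 0.00145 + 1.05 × 2.95 × 10⁻⁴ = 0.00176, so SE = 0.0419. B/m = 1.475 × 10⁻⁵ and SD(SE) = 0.00120. The SD is √(1.475 × 10⁻⁵ + 0.55 × 10⁻⁵) = 0.0045, or 0.45 points.
- Per subject: SE = 0.0413 and SD = √(1.23 × 10⁻⁵ + 0.39 × 10⁻⁵) = 0.0040, or 0.40 points.

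Simulation agrees. The SAP's procedure gave 0.41 points, and two simulations of joint imputation gave 0.44 and 0.46. The sampling SE is about 4.1 points, so the noise is about one tenth of it.

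**Step 4: other missing fractions and larger m.** SD of the lower bound in percentage points, by the formula of step 3 (per subject / joint):

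| Missing | m = 20 | m = 100 | m = 500 |
|---|---|---|---|
| 10% | 0.30 / 0.32 | 0.13 / 0.14 | 0.06 / 0.06 |
| 16.9% | 0.40 / 0.45 | 0.18 / 0.20 | 0.08 / 0.09 |
| 20% | 0.44 / 0.51 | 0.20 / 0.22 | 0.09 / 0.10 |

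**Step 5: effect on the verdict.** If the noise-free bound lies a distance d from -12.5%, a seed puts it on the other side with probability Φ(−d/0.41): 31% at 0.2 points, 16% at 0.4, 2.6% at 0.8 and 0.2% at 1.2.

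Over whole simulated trials at 16.9% missing, two seeds gave opposite verdicts in 3.3% (true difference 0) and 4.5% (true difference -4.4 points). A separate simulation with 4,000 trials per scenario gave 3.4% at 0, 4.8% at -3 and 4.1% at -4.5 points.

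A hand check: the probability is roughly the density of the bound at -12.5%, times 2s/√π, with s = 0.41 (2s/√π = 0.463).

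- True difference 0: the simulated bound has mean -8.52 and SD 4.28, so the density is 0.0605 per point and the result 2.8%.
- True difference -4.4: mean -13.04 and SD 4.23, so the density is 0.0936 and the result 4.3%.

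**The case against.** Three stronger readings are tempting, and the documents do not support them.

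- **Two runs of the same plan could disagree.** A reader might infer this from the noise. But SAP 8.4.1 fixes seeds and order so that results can be replicated exactly. At m = 20, a run with another seed is not a run of this plan, and nobody can pick a seed after seeing results.
- **m has simply been left unset.** The code and its text say 20 throughout 8.4.1, and 8.2.8 states m = 20 for DOOR. What remains is one sentence at odds with the rest. The trigger it names is the missing percentage, not the treatment effect, so it is not a route to a favourable answer. Nor does the open wording cause the noise; m = 20 does.
- **Inference is invalid at m = 20.** Rubin's rules widen the interval for finite m, and nothing here shows bias, undercoverage or an inflated type I error. Adding the noise to the sampling SE gives √(4.1² + 0.41²) = 4.12, an increase of about 0.5%.

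It is also fair to say that the missing-data assumption matters more than the seed. In the tipping-point grid of Table 27, each 20-point step in one arm moves the difference by 0.20 × 57/337 = 3.4 points. And 16.9% is ATP-5 loss, which includes adherence and rescue-medication exclusions, so missing Day 5 outcomes in the ITT population could be fewer.

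What survives is narrow. A fixed seed makes the answer repeatable but no less arbitrary; another integer would have served equally well. Seeds are also tied to position in the list of imputed subjects, so adding or removing one subject before lock changes the seed of every later subject. Neither the tipping-point grid nor the ATP-5 analysis without imputation measures this noise.

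**Conclusion.** The point holds as a minor one. At m = 20 the only confirmatory bound has a Monte Carlo SD of about 0.30 points at 10% missing and 0.41 to 0.46 at 16.9%. An arbitrary but prespecified seed could settle the verdict if the bound falls within about 0.8 points of -12.5%; the 3 to 5% figure is how often two seeds disagreed across simulated trials. Separately, the narrative and the code of SAP 8.4.1 should agree on m.

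This rests on outcomes missing at random, covariates that predict the outcome weakly, a 57.6% improvement rate in the azithromycin arm, and a missing fraction between 10% and 20%. Less missing data would shrink the noise.

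**What to change.** Before unblinding:

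1. In SAP 8.4.1, delete the clause that leaves m to be chosen from the percentage missing, and state one fixed value.
2. Use that value in the narrative, the pseudo-code and the pooling step, for D5V, D11V and D28V. At least 100 brings the SD to about 0.2 points; about 500 brings it under 0.1. The documents set no tolerance, so the choice between these is a judgement.
3. Use the same m for DOOR in SAP 8.2.8 and 8.4.2.
4. Keep the prespecified seeds and processing order.
5. Report the Monte Carlo standard error of the lower bound with Table 21.

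The cost is a few lines of SAP text and some minutes of computing. No patients, data or procedures are affected.

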### 9.5.2 Individual Halting Rules (Termination of Study Product Administration)

Study product administration may be discontinued if any of the following criteria are met:

- Any clinical adverse event (AE), intercurrent illness, or other medical condition occurs that, in the opinion of the investigator, continued receipt of study product would not be in the best interest of the subject;
- New onset of illness or condition that meets exclusion criteria, at the investigator's discretion
- Inadequate clinical response that requires off-study antimicrobial therapy.
  - Subjects who require off-study antimicrobial therapy will be defined as having an inadequate clinical response.

Subjects may stop study drug treatment at any time of their own volition or at the advice of their treating provider or the study investigators. Subjects who stop study product for any reason will be regarded as having withdrawn from treatment but not as having withdrawn from the study (i.e, subjects will be asked to continue to participate in follow-up visits). All subjects with an inadequate clinical response will be referred to a non-study healthcare provider for evaluation and possible treatment outside of the clinical study. If requested, unblinding can occur if clinically indicated as determined by the treating clinician and the study's site investigator.

At the time of withdrawal, subjects will undergo an early termination visit if they are not willing to participate in the remaining follow-up visits.

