6.3. Analysis Populations

The primary analysis will be done using the intention-to-treat (ITT) cohort. Other analyses may use according-to-protocol (ATP) cohorts. Analyses of the ITT cohort will include imputation for missing clinical improvement and DOOR.

Reasons for exclusion from each analysis population are summarized in [Table 9](#) and shown by subject in [Listing 5](#). Excluded subjects might satisfy multiple criteria justifying their exclusion but will have only one reason indicated in [Table 9](#) and [Listing 5](#). The exclusion reason indicated will be determined by first exclusion reason met based on the following rules in the order they are listed for each analysis population.

Safety Population Exclusions:

- Subject not treated with any dose of study product

ITT Population Exclusions:

- Non-randomized subjects

ATP Population Exclusions:

- Subject was excluded from ITT
- Subject had major protocol deviation related to I/E criteria
- Did not consume 5 doses of study product by D5V
- First dose of study product not taken within 24 hours of randomization
- Dosing not resumed within 24 h of a missed dose

ATP-5 Population Exclusions:

- Subject was excluded from ATP population
- Subject did not complete D5V
- D5V occurred out of the protocol defined window of Day 5 + 3 days
- D5V was not completed in person
- Data collected is insufficient to define clinical improvement at D5V

ATP-11 Population Exclusions:

- Subject was excluded from ATP population
- Subject did not complete D11V
- D11V occurred out of the protocol defined window of Day 11 + 3 days
- Data collected is insufficient to define clinical improvement at D11V

ATP-28 Population Exclusions:

- Subject was excluded from ATP population
- Subject did not complete D28V
- D28V occurred out of the protocol defined window of Day 28 ± 2 days
- Data collected is insufficient to define clinical improvement at D28V

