8.2. Secondary Efficacy Analyses

8.2.1. Analyses of Clinical Improvement at D5V using ATP-5 Analysis Population.

The ATP-5 analysis population will have no missing values of clinical improvement, therefore the analysis of clinical improvement at D5V will be performed using a linear regression without multiple imputation with treatment group and centered study day of D5V as a covariates ($Y_i = \beta_0 + \beta_1 trt_i + \beta_2 cstday5 + \epsilon_i$) for subjects in the ATP-5 analysis population. The rate of clinical improvement in the placebo group will then be

estimated by $p_p = \beta_0 + \beta_1$ and the rate of clinical improvement in the azithromycin arm will be provided by $p_a = \beta_0$ assuming that the study day of D5V is 5.

The estimate for the difference in rates of clinical improvement given that study day of D5V is 5 will be provided by β_1 and its 95% CI will be calculated first by using the 95% CI for β_1 from the linear regression model above. As a sensitivity analysis, the 95% CI for the difference in rates of clinical improvement will be recalculated using the Miettinen–Nurminen (MN) method [13] from PROC FREQ with RISKDIFF (CL=MN) in SAS without adjusting for study day of D5V.

Rates of clinical improvement for each treatment group, a point estimate of the difference in rates of clinical improvement at D5V along with their 95% CIs obtained methods described above will be provided in [Table 22](#) using the ATP-5 analysis population. If the lower bound of the 95% CI for the difference in rates of clinical improvement is greater than -12.5%, it will be annotated by a footnote c.

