  monotone regression(clinimprove_D5V) = &&modelVars_&i;
```

```
run;
```

```
%end;
```

imp_g&i will be subset to contain only rows for the subjects with imputed clinical improvement and merged together and with ATP-5 data to create the twenty complete multiply imputed datasets

Step 2: Analysis model: This model will fit regression models to the 20 complete datasets to obtain parameter estimates for treatment success, clinical cure, microbiological success.

```
proc reg data= imp_g outest= out_clinimp_D5V covout noprint;
```

```
model clinimprove_D5V= trt cstday5/clb alpha=0.05;
```

```
by _imputation_;
```

```
run;
```

Step 3: Combine estimates from models in step 2 to obtain overall estimates summarized over 20 imputed datasets;

```
proc mianalyze data= out_clinimp
```

```
  _D5 alpha = 0.05;
```

```
modeleffects intercept trt cstday5;
```

```
ods output ParameterEstimates=parms_trts;
```

```
run;
```

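### SAP 8.4.1 is wrong as written: its code builds the ITT primary datasets from ATP-5 rows, so some observed Day 5 outcomes are dropped or overwritten

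*SAP*

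**What the plan says.** **Population.** Protocol 11.4 and 11.4.1 place the primary analysis in the ITT population of everyone randomised. SAP 5 agrees: "the primary analysis will be an ITT analysis using all randomized subjects". SAP 6.3.1 and 8.1.1 impute only missing values, and the Table 21 shell sets N to the ITT population and counts all non-missing Day 5 outcomes.

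**Code.** SAP 8.4.1 loops over the subjects who need imputation. The dataset used to fit each model (g&i) holds "ATP-5 subjects as well as subject i (only one subject not in ATP-5 included". After the loop, "imp_g&i will be subset to contain only rows for the subjects with imputed clinical improvement and merged together and with ATP-5 data". Step 2 runs the primary regression on the result. The Step 1 line of the same block describes a different product, "each dataset containing original complete data along with imputed values for subjects with missing endpoint".

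**ATP-5.** SAP 8.2.1 states: "The ATP-5 analysis population will have no missing values of clinical improvement". But SAP 6.3 also removes subjects for reasons unrelated to whether the outcome was recorded. Examples are "Did not consume 5 doses of study product by D5V", a late first dose, dosing not resumed in time after a missed dose, and a Day 5 visit not done in person.

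**Follow-up after stopping.** Protocol 9.5.2: "Subjects who stop study product for any reason will be regarded as having withdrawn from treatment but not as having withdrawn from the study".

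**The concern.** ATP-5 is narrower than the set of subjects whose outcome was observed. A subject who stops product early but attends Day 5 in the window has an outcome, needs no imputation, and is not in ATP-5. The code as written has no place for that subject, although the ITT definition includes them.

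SAP 8.1.1 lets the primary analysis alone decide non-inferiority, so its row set should not depend on how a programmer resolves one label. On the literal code the observed part of the ITT analysis is exactly the ATP-5 population. The model is also fitted on ATP-5 only, so outcomes observed outside ATP-5 do not inform the imputed values.

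**Working it through.** **1. Planned size of the group outside ATP-5.** SAP 5 and 6.6 give 560 in ATP-5 and 16.9% loss. 560 / (1 − 0.169) = 673.9, which reproduces the stated 674. Outside ATP-5: 674 − 560 = 114.

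**2. Set logic.**
- ITT = {outcome missing} ∪ {outcome observed}.
- Literal datasets = {outcome missing} ∪ {ATP-5}.
- The difference is k subjects with an observed in-window outcome who are outside ATP-5. Each dataset has 674 − k rows, so between 560 and 674 on planned figures. The documents do not give k.
- Out-of-window visits do not count towards k, because SAP 3.3.1 sets them to missing. Eligibility deviations do not either, because SAP 6.3.2 reports that none led to ATP exclusion. Dosing and visits not done in person remain, the latter where the outcome can still be defined.

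**3. Second reading.** If everyone outside ATP-5 is imputed, all 674 rows are present, but observed outcomes are replaced by imputed ones. That contradicts SAP 6.3.1 and 8.1.1.

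**4. Bias on the literal reading.** Let an arm have ITT rate r, dropped share f, and success rate s among the dropped. The retained rate is (r − f·s)/(1 − f), a shift of f(r − s)/(1 − f). The bias in placebo minus azithromycin is the placebo shift minus the azithromycin shift. It is zero when the dropped subjects match their own arm's rate.

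**5. Illustration.** Assumed: 337 per arm, azithromycin 57.6%, and a true difference at the margin, so placebo 45.1%. Dropped shares are 4% (13 subjects) or 8% (27). With all dropped subjects failing (s = 0) and no missing data, at 4% azithromycin and 8% placebo:
- azithromycin 0.576/0.96 = 0.600; placebo 0.451/0.92 = 0.490; difference −0.110
- SE = √(0.600·0.400/323.5 + 0.490·0.510/310.0) = 0.0393
- false non-inferiority = Φ((0.125 − 0.1098)/0.0393 − 1.96) = Φ(−1.57) = 5.8%

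The same formula for each split:

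| Dropped, azithromycin / placebo | Rows | Difference if all fail | All fail | 70% fail | Own arm's rate |
|---|---|---|---|---|---|
| 4% / 4% | 648 | −13.0 | 1.8% | 1.8% | 2.5% |
| 4% / 8% | 634 | −11.0 | 5.8% | 2.8% | 2.5% |
| 8% / 4% | 634 | −15.6 | 0.3% | 0.8% | 2.5% |
| 8% / 8% | 620 | −13.6 | 1.3% | 1.3% | 2.5% |

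**6. Check by simulation.** The remainder of the 16.9% was set missing at random and imputed by linear regression as in 8.4.1 (m = 20, 6,000 trials per scenario, Monte Carlo SE about 0.2 points at 2.5%). Only treatment and visit day were modelled, with an assumed visit-day mix. In the row order of the table, the literal code gave:
- all fail: 2.0, 5.8, 0.3 and 1.3%
- 70% fail: 2.0, 2.8, 0.9 and 1.3%
- own arm's rate: 2.4 to 2.8%

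With the label corrected, error was 2.0 to 2.7% and the mean estimate −12.4 to −12.6 throughout.

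**The case against.** The strongest reply is that the intent is clear and a competent programmer would follow it. Protocol 11.4 and SAP 5, 6.3.1, 8.1.1 and Table 21 all say ITT. The Step 1 line describes the right dataset. The DOOR code in 8.4.2 uses a complete-case label, CC-D5, in the same position. The block also carries text that does not belong to this trial, such as clinical cure and microbiological success, so it needs correcting against the prose anyway. What 8.4.1 says must be followed is the seeds and the processing order, not the population label. Planned output would also expose the gap: Table 21's non-missing count minus Table 22's ATP-5 N gives k.

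Most of this stands. It makes a drafting slip the likely explanation. It does not make the code right, and counting k afterwards would not correct the estimate.

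A reader might infer that the dropped rows are mainly rescued placebo failures, so that the code favours placebo. The documents do not support that. Protocol 9.5.2 does list "Inadequate clinical response that requires off-study antimicrobial therapy" as a reason for which product may be stopped, and SAP 5 mentions rescue medication within the 16.9% loss. But rescue is not itself an ATP exclusion in SAP 6.3, a rescued subject who takes all five doses on schedule stays in, and the only stated loss is the same in each arm.

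**Conclusion.** Wrong as written. The fitting and merge lines in SAP 8.4.1 contradict the ITT definition and the Step 1 line of the same block. Either way of programming them literally breaks the stated plan: observed outcomes are left out or overwritten.

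Size and direction are unknown, because the documents give neither the number, the arm split nor the failure rate of the affected subjects. Of the 12 assumed scenarios, one clearly exceeds the nominal 2.5%: 5.8%, with every dropped subject failing and twice the share dropped on placebo. The other 11 are neutral or conservative within simulation error (0.3 to 2.8%). The grid is not a bound. By the formula in step 4, a larger placebo share, or a worse outcome among placebo drop-outs than among azithromycin ones, pushes in the same direction.

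Two stronger inferences go too far: that the planned primary analysis is not ITT, and that its error rate is inflated. The prose settles the first against the code, and the second depends on figures that the documents do not contain.

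**What to change.** In SAP 8.4.1, in the definition of g&i and in the merge line, replace *ATP-5* with *all ITT subjects with observed clinical improvement at D5V*. Make the same change for D11V and D28V, to which the SAP extends the code.

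Add a program check that each completed dataset has as many rows as the ITT N in Table 21. The row count detects dropped subjects but not overwritten ones, so the number imputed should also equal the missing count in Table 20.

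The cost is a few words of SAP text and one or two program lines. The imputation models and seeds can stay, and no new data or subjects are needed.
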